3. OBJECTIVES/ENDPOINTS

3.1. Primary Objective

- To determine the incidence of AFI due to Laboratory Confirmed Dengue (LCD) in the study population.

3.2. Secondary Objectives

- To determine the incidence of AFI due to non-LCD in the study population.
- To describe the signs and symptoms of AFI due to LCD and of AFI due to non-LCD.
- To estimate the incidence of AFI due to LCD by Dengue Virus (DENV) type, , study site and age group.

3.3. Tertiary Objectives

- To describe DENV and Japanese Encephalitis Virus (JEV) antibody profiles in subsets of subjects with AFI.
- To assess the concordance between dengue Reverse transcriptase-quantitative Polymerase Chain Reaction (RT-qPCR) and Non-Structural protein 1 (NS1)-antigen Immuno Chroma Tographic (ICT) test and/or Enzyme-Linked Immunosorbent Assay (ELISA) in the assessment of dengue infection.
- To gather clinical data that will support the definition of clinical endpoints for future efficacy trials.
- To describe spatio-temporal clustering of LCD cases.
- To describe entomological characteristics at selected site(s).
- To estimate the prevalence and incidence of tuberculosis diagnosis in the study population.
- To describe the incidence of hospitalisation and discharge diagnosis in the study population.
- To isolate and characterise infectious agents from a subset of subjects with AFI.
- To evaluate the antibody response to infectious agents in a subset of subjects with AFI.

3.4. Primary endpoint

- Occurrence of AFI due to LCD.

3.5. Secondary endpoints

- Occurrence of AFI due to non-LCD.
- Occurrence and intensity of signs and symptoms of interest, during the 7-day period following the onset of each episode of AFI due to LCD and due to non-LCD.
- Occurrence of AFI due to LCD by DENV type, study site and age group.

3.6. Tertiary endpoints

The following is a list of planned tertiary analyses. Per protocol, tertiary study endpoint assays other than dengue serology *may be* performed for a subset of samples (for example, JEV assays will only be conducted if additional studies indicate that JEV serology is needed to interpret the DENV antibody).

Refer to section 8 for information regarding tertiary analyses that will not be performed.

- Neutralising antibody titres against DENV 1-4.
- Neutralising antibody titres against JEV.
- Neutralising antibody titres against other viruses, including but not limited to, Chikungunya virus.
- Incidence of NS1-antigen (ICT test and/or ELISA)-positive AFI by DENV type.
- Concordance between dengue RT-qPCR and NS1-antigen (ICT and/or ELISA) assays.)
- Occurrence of AFI due to LCD and due to non-LCD having ≥ 3 days of fever (body temperature $\geq 38^{\circ}\text{C}/\geq 100.4^{\circ}\text{F}$).
- Occurrence of AFI due to LCD and due to non-LCD resulting in hospitalisation.
- Occurrence of combinations of signs and symptoms during the 7-day period following the onset of each episode of AFI due to LCD and due to non-LCD.
- Occurrence of AFI due to LCD within 2 weeks from an index case, in the same household or within 50 metres of the household of the index case.
- Entomological characteristics for LCD cases (e.g., vector species, density and number of breeding sites)
- Occurrence (by medical history only) of a diagnosis of tuberculosis, from birth up to study conclusion, in the study population.
- Occurrence of hospitalisation and discharge diagnosis.
- Identification and characterisation of infectious agents isolated from blood (e.g., DENV, influenza viruses, chikungunya viruses), in subjects with AFI.

4. ANALYSIS SETS

4.1. Definition

4.1.1. Total Cohort

The Total cohort will include all subjects enrolled in the study.

4.1.2. Total Cohort without subjects with code 900

The Total cohort without subjects with code 900 will include all subjects from the Total cohort excluding subjects with elimination code 900.

This cohort will be used only if a code 900 is attributed. In this case, this cohort will replace the Enrolled cohort in all statistical analyses.

4.2. Criteria for eliminating data from Analysis Sets

Elimination codes are used to identify subjects to be eliminated from analysis. Details are provided below for each set.

4.2.1. Elimination from Total Cohort without subjects with code 900

Code 900 (invalid informed consent or fraud data) will be used for identifying subjects eliminated from the Total cohort without subjects with code 900.

5. STATISTICAL ANALYSES

That standard data derivation rules and statistical methods are described in section xx while the study specific data derivation rules and statistical methods are described in section xx.

5.1. Demography/baseline characteristics

5.1.1. Analysis of demographics/baseline characteristics planned in the protocol

Socio-demographic and patient characteristics (e.g., age at study enrolment, gender, household conditions, medical history and vaccination history) will be summarized overall and for LCD cases using descriptive statistics:

- Frequency tables will be generated for categorical variable such as gender.
- Mean, median, standard deviation will be provided for continuous data such as age.

5.2. Primary objective

5.2.1. Analysis of primary objective planned in the protocol

The incidence rate of first AFI due to LCD will be calculated along with 95% exact confidence interval. This analysis will be based on the total enrolled set. See section 9.2.1 and section 9.2.2 for details of incident rate and confidence interval calculation respectively.

5.2.2. Additional Consideration

Additional case definition of AFI was added to the analysis. See Table 2 for details of ad-hoc case definitions. Incidence rate along with 95% exact confidence interval of AFI based on the ad-hoc case definition due to LCD will be calculated.

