3. STUDY DESIGN OVERVIEW

Protocol waivers or exemptions are not allowed. Therefore, adherence to the study design requirements, including those specified in the outline of study procedures (Section 6.4), are essential and required for study conduct.

Figure 1 Study design overview

[figure not shown]
Scheduled Visits

- Visit 1 and Visit 2 will take place **at home or** at the hospital/clinic
- Weekly contacts will be home visits (at least every other week) or **telephone contacts (TCs)**

Unscheduled Visits

- Suspected Dengue First Visit (hospital/clinic)
- Optional Return Visit (hospital/clinic)
- Suspected Dengue Follow-up Visit (hospital/clinic or home)

Notes: (Amended 01 March 2017)

The weekly contact may be a face to face visit outside the home in certain cases (i.e. at hospital during suspected dengue visit)

An unscheduled visit (either for first, return, or follow-up dengue visit) will be considered as the weekly contact for the week in which it occurs.

- **Type of design:** Prospective, community-based, cohort study, household-sampling, **single country.** (Amended 01 March 2017)
- **Study population:** Approximately **2000** subjects aged between 6 months and 50 years at the time of enrolment living in randomly selected households in geographically-defined communities. Households including at least one member aged less than 18 years will be considered eligible if at least one adult (aged no more than 50 years) and one child (aged less than 18 years) consent (and assent if applicable) to participate in the study. (Amended 01 March 2017)

- **Study visits:** The study will consist of scheduled visits (the enrolment visit [Visit 1], weekly contacts, and the close-out visit [Visit 2]) and, in case of AFI*, unscheduled Suspected Dengue Visits:
 - Visit 1 and Visit 2 will take place at home or at the hospital/clinic, in accordance with local ethics committee requirements and/or national laws or regulations
 - Weekly contacts will be home visits (at least every other week) or telephone contacts (TCs). *The weekly contact may be a face to face visit outside the home in certain cases (i.e. at hospital during suspected dengue visit)*
(Amended 01 March 2017)
 - Unscheduled Suspected Dengue Visits will take place in case of AFI*

*AFI is defined as fever (body temperature $\geq 38^{\circ}\text{C}/\geq 100.4^{\circ}\text{F}$) on ≥ 2 consecutive calendar days, measured at least twice, at least 8 hours apart.

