The subject/subject's parent(s)/LAR(s) will bring the diary card with him/her to each Suspected Dengue Visit. The investigator or appointed study personnel will review the diary card information with the subject and will record the information in the eCRF if a temperature of $\geq 38^{\circ}\text{C}$ ($\geq 100.4^{\circ}\text{F}$) was recorded on ≥ 2 consecutive calendar days, measured at least twice, at least 8 hours apart. The subject/subject's parent(s)/LAR(s) will return the diary card when completed at the next visit or contact (i.e., at the next home visit or at a Suspected Dengue Visit).

Note: Diary cards can be filled in by a minor subject under the supervision of the subject's parent(s)/LAR(s) provided that the minor has the competence to assess and report the information to be provided on the diary card. The ultimate accountability for the completion of the diary cards remains with the subject's parent(s)/LAR(s). The investigator should discuss this accountability with the subject's parent(s)/LAR(s).

Note: If the diary card has been filled in by a minor subject, the investigator or delegate should verify the reported information during a discussion with the minor subject preferably in the presence of his/her parent(s)/LAR(s).

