- If a subject or subject's parent/LAR reports fever (body temperature $\geq 38^{\circ}\text{C}/\geq 100.4^{\circ}\text{F}$) during any home visit or TC, the local study coordinator will arrange for a Suspected Dengue First Visit at the designated study hospital/clinic for medical evaluation and blood sampling (refer to Section 6.5.5.1). The Suspected Dengue First Visit should be scheduled within 7 days from the onset of fever (Days 2-7) and should ideally take place on the second day of fever (Day 2). If the visit has not taken place within the 7-day period (Days 2-7) from the onset of fever, it is no longer required and the case will be considered as an undetermined case.
- Collection and distribution of diary cards as needed (only applicable for home visits).
- Recording of diary cards information by the investigator.

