6.5.4.3. Recording of serious adverse events related to study participation

Refer to Section 6.5.2.6.

6.5.5. Procedures at Suspected Dengue Visits**6.5.5.1. Procedures at Suspected Dengue First Visit*****6.5.5.1.1. Important general remarks***

All study subjects with AFI (fever [body temperature $\geq 38^{\circ}\text{C}/\geq 100.4^{\circ}\text{F}$] on ≥ 2 consecutive calendar days, measured at least twice, at least 8 hours apart) should be seen at a designated study hospital/clinic by the study physician. The Suspected Dengue First Visit should be scheduled within 7 days from the onset of fever (Days 2-7) and should ideally take place on the second day of fever (Day 2).

If a subject with fever (body temperature $\geq 38^{\circ}\text{C}/\geq 100.4^{\circ}\text{F}$) on ≥ 2 consecutive calendar days, measured at least twice, at least 8 hours apart has not been evaluated at a Suspected Dengue First Visit (or directly in a hospital/clinic) within the 7-day period (Days 2-7) from the onset of fever, the Suspected Dengue First Visit is no longer required and the case will be considered as an undetermined case. If a diary card has been filled, the data needs to be recorded in the eCRF.

Blood samples for study procedures should not be drawn from subjects who attend a study healthcare facility on the first day of fever (body temperature $\geq 38^{\circ}\text{C}/\geq 100.4^{\circ}\text{F}$), i.e., on Day 1. Medical assistance can be provided to these subjects but they will be asked to come back the following day should the fever persist. Blood samples for study procedures should only be drawn from the second day of fever (i.e., from Day 2, the second calendar day with fever) and onwards, up to Day 7.

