6.5.5.1.4. Blood sampling

Blood samples should only be drawn in case of AFI (i.e., fever [body temperature $\geq 38^{\circ}\text{C}/\geq 100.4^{\circ}\text{F}$] on ≥ 2 consecutive calendar days, measured at least twice, at least 8 hours apart) during the Suspected Dengue First Visit from the second day of fever (i.e., from Day 2, the second calendar day with fever) and onwards, up to Day 7.

The following blood samples should be collected unless an obvious alternative diagnosis, i.e., an obvious cause of fever other than dengue, has been identified and is documented (Amended 01 March 2017):

- Whole blood for laboratory confirmation of dengue by NS1-antigen (ICT test and/or ELISA): 0.5 mL, from all subjects (any age). The results of this/these test(s) should be recorded in the eCRF.
- Whole blood for laboratory confirmation of dengue infection by (generic and/or serotype-specific) RT-qPCR: 2.5 mL, from all subjects (any age).

- Whole blood for haematology assessment (complete blood count): 2 mL, from all subjects \geq 5 years of age and from subjects $<$ 5 years of age only if clinically indicated, as per investigator judgement or local recommendations. The results of these tests should be recorded in the eCRF.
- Whole blood for other tertiary (research) endpoints related tests (including, but not limited to, neutralising antibody against JEV and Chikungunya virus, tissue culture to isolate infectious agents, and sequencing to characterise infectious agents): **3.5 mL**, from all subjects \geq 18 years of age. A subset of these samples will be tested.

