6.7. Biological sample handling and analysis

Biological samples will only be taken in case of AFI (i.e., fever [body temperature $\geq 38^{\circ}\text{C}/\geq 100.4^{\circ}\text{F}$] on ≥ 2 consecutive calendar days, measured at least twice, at least 8 hours apart), during the Suspected Dengue First Visit.

Please refer to the SPM for details of biospecimen management (handling, storage and shipment).

Samples will not be labelled with information that directly identifies the subjects but will be coded with the identification number of the subject (subject number and Visit number).

- Collected samples will be used for protocol mandated research. In addition, these samples may be used to perform research related to the improvement, development and quality assurance of the laboratory tests described in this protocol. This may include the management of the quality of these tests, the maintenance or improvement of these tests, the development of new test methods, as well as making sure that new tests are comparable to previous methods and work reliably.

- It is also possible that future findings may make it desirable to use the samples acquired in this study for future research, not described in this protocol. Therefore, all subjects in countries where this is allowed will be invited to give another specific consent to allow GSK or a contracted partner use the samples for future research including development of tests and their quality assurance. Future research will be subject to the laws and regulations in the respective countries and will only be performed once an independent Ethics Committee or Review Board has approved this research.

Information on further investigations and their rationale can be obtained from GSK Biologicals.

Any sample testing will be done in line with the consent (and assent if applicable) of the individual subject/subject's parent(s)/LAR(s).

Refer also to the [Investigator Agreement](#), where it is noted that the investigator cannot perform any other biological assays except those described in the protocol or its amendment(s).

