9. NON-STANDARD DATA DERIVATION RULES AND STATISTICAL METHODS

9.1. Data derivation

9.1.1. Case Definition

The different case definitions for febrile illness are summarized in Table 2

Table 2 Summary of case definitions

Endpoint	Case definition	Case definition for ad-hoc Analysis
AFI with LCD	
[Fever (body temp \geq 38 C /100.4 F) on at least 2 consecutive days are measured at least twice, at least twice 8 hours apart
 
AND
 
Dengue RT-qPCR result on the acute serum sample taken during the 7-day period from onset of fever is positive
	
[Fever (body temp \geq 38 C /100.4 F) on at least 2 consecutive days are measured at least twice, OR
 
Fever (body temp \geq 38 C /100.4 F) on at least 1 day is measured at least twice 8 hours apart
 
AND
 
Clinical suspicion of dengue base on solicited symptoms],
 
AND
 
Dengue RT-qPCR result on the acute serum sample taken during the 7-day period from onset of fever is positive

DENV – 1 LCD	
[Fever (body temp \geq 38 C /100.4 F) on at least 2 consecutive days are measured at least twice, at least twice 8 hours apart
 
AND
 
Dengue 1 specific RT-qPCR result during the 7-day period from fever is positive
	
[Fever (body temp \geq 38 C /100.4 F) on at least 2 consecutive days are measured at least twice, OR
 
Fever (body temp \geq 38 C /100.4 F) on at least 1 day is measured at least twice 8 hours apart
 
AND
 
Clinical suspicion of dengue base on solicited symptoms],
 
AND
 
Dengue 1 specific RT-qPCR result during the 7-day period from fever is positive

Endpoint	Case definition	Case definition for ad-hoc Analysis
DENV – 2 LCD	
[Fever (body temp \geq 38 C /100.4 F) on at least 2 consecutive days are measured at least twice, at least twice 8 hours apart
 
AND
 
Dengue 2 specific RT-qPCR result during the 7-day period from fever is positive
	
[Fever (body temp \geq 38 C /100.4 F) on at least 2 consecutive days are measured at least twice, OR
 
Fever (body temp \geq 38 C /100.4 F) on at least 1 day is measured at least twice 8 hours apart
 
AND
 
Clinical suspicion of dengue base on solicited symptoms], AND
 
Dengue 2 specific RT-qPCR result during the 7-day period from fever is positive

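### The SAP's ad-hoc dengue rate is only a lower bound, because detection, blood sampling and diary entry follow the stricter protocol definition of AFI

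*SAP*

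**What the plan says.** **The ad-hoc analysis.** SAP 5.2.2 commits to this: "Incidence rate along with 95% exact confidence interval of AFI based on the ad-hoc case definition due to LCD will be calculated". In SAP Table 2 (section 9.1.1) the ad-hoc column has two fever arms. One is fever on two consecutive days with two readings and no 8-hour gap. The other is fever "on at least 1 day is measured at least twice 8 hours apart". Clinical suspicion based on solicited symptoms follows, then the RT-qPCR result. The text does not say whether suspicion applies to both arms or only to the second.

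**The protocol's AFI definition.** Protocol section 3 requires fever on two or more "consecutive calendar days, measured at least twice, at least 8 hours apart".

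**Who is bled.** Protocol 6.5.5.1.4 and the Table 3 footnote both say: "Blood samples should only be drawn in case of AFI". Protocol 6.7 says: "Biological samples will only be taken in case of AFI". For subjects seen on the first day of fever, 6.5.5.1.1 rules out study blood and says "they will be asked to come back the following day should the fever persist".

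**What is recorded.** Under 6.5.2.5, staff review the diary card and "will record the information in the eCRF if a temperature of" 38°C or more meets the full AFI pattern. Section 6.5.5.1.5 applies the same condition at the First Visit.

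**Wording that points the other way.** Protocol 6.5.3.2 begins "If a subject or subject's parent/LAR reports fever", with no AFI condition, and arranges a First Visit that includes blood sampling. Protocol section 3 has blood taken at every Suspected Dengue First Visit, and SAP section 2 at every suspected dengue visit.

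**The concern.** The ad-hoc definition can add to the protocol LCD count only through episodes that fall short of AFI, and those episodes need a PCR-positive sample. The protocol does not set out to obtain that sample systematically. It also does not routinely record the diary symptoms on which clinical suspicion would rest. Any gain over the primary rate therefore depends on how many such episodes happened to be bled, a fraction that neither document gives.

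This matters because the study is meant to inform case definitions for later efficacy trials (Protocol 2.3 and 3.1). A near-zero increment could come from the sampling rule alone, yet be taken as evidence that broadening the definition adds little. SAP section 8 does not mention the limitation.

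**Working it through.** **1. Which episodes can be added, and how they meet the protocol's rules**

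| Step | Protocol rule | Two days, no 8-hour gap | At least one day, plus suspicion |
|---|---|---|---|
| Subject told to make contact (6.5.2.5) | On AFI | Outside | Outside |
| Weekly question (6.5.3.1) | About AFI | Outside | Outside |
| Blood draw (6.5.5.1.4, 6.7, Table 3 footnote) | AFI, Days 2 to 7 | Outside | Outside |
| Blood by day of fever (6.5.5.1.1) | From the second day of fever | Would be admitted | No draw on Day 1; return only if fever persists |
| Diary data to eCRF (6.5.2.5, 6.5.5.1.5) | If AFI is met | Not routine | Not routine |
| Any reported fever (6.5.3.2) | First Visit with blood sampling, cross-referring to 6.5.5.1 | Possible route to a sample | Possible route to a sample |

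Sampling of ad-hoc-only episodes is thus neither ruled out throughout nor systematic.

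**2. The plan's own precision figures**

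The exact limits in Protocol Table 17 are χ²(0.025; 2n)/(2·PY) and χ²(0.975; 2n+2)/(2·PY). With n = 40 and PY = 3300 the rate is 1.21 per 100 person-years, with limits 0.87 and 1.65. All ten rows reproduce to two decimals. The stated dropout gives 2000 × 0.9 + 2000 × 0.9 × 0.8 = 3240 person-years, within 3% of 3300.

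**3. Effect of incomplete sampling**

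Let P be the protocol LCD cases, E the true extra PCR-positive cases under the ad-hoc definition, and s the fraction of E that was sampled.

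- Reported rate = (P + s·E)/PY
- True rate = (P + E)/PY
- Share of the extra yield that is seen = s

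Take P = 40 (a row of Table 17) and PY = 3300. E and s are assumptions. Rates are per 1000 person-years, the SAP's unit.

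| E | s = 0 | s = 0.25 | s = 0.5 | True rate |
|---|---|---|---|---|
| 10 | 40/3300 = 12.1 | 42.5/3300 = 12.9 | 45/3300 = 13.6 | 50/3300 = 15.2 |
| 20 | 40/3300 = 12.1 | 45/3300 = 13.6 | 50/3300 = 15.2 | 60/3300 = 18.2 |

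Person-years are held fixed. Ending follow-up at 20 extra events removes at most about 20 × 2 = 40 person-years, roughly 1%.

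**4. What the exact interval covers**

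The interval reflects Poisson variation in the cases counted, not cases never tested. With s = 0, Table 17 gives 8.7 to 16.5 per 1000 for 40 cases, which excludes the assumed true rate of 18.2.

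**5. Order of OR and AND**

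Read as [(two-day arm) OR (one-day arm AND suspicion)] AND RT-qPCR, every protocol LCD case meets the two-day arm and is retained. Read as [(either arm) AND suspicion] AND RT-qPCR, a protocol LCD case without recorded suspicion drops out, and the broader rate could fall below the primary one.

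**The case against.** The other side has good arguments.

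- **A reader might infer that no ad-hoc-only episode may be bled.** The documents do not support that. Protocol 6.5.3.2, Protocol section 3 and SAP section 2 give a competing route to a sample. A subject with fever on two calendar days may also be bled in good faith and later fail the 8-hour test on the recorded readings, since twice-daily measurement is only the ideal (6.6.1). That last step is an inference; no count is given. These routes make s greater than zero in places, but they do not make ascertainment complete.
- **A reader might infer that the ad-hoc rate consists only of off-protocol samples.** It does not. Under the bracketing that retains protocol cases, all protocol LCD cases are in the numerator, and only the increment is in doubt.
- **Symptom data are not wholly absent.** First Visit examination findings go into the eCRF (6.5.5.1.2), and hospital or clinic records can update clinical data (6.5.3.2). Capture is incomplete rather than missing.
- **The SAP claims little.** SAP section 6 calls all analyses descriptive, and 5.2.2 does not say that it estimates the yield of a broader definition. That stands, but a descriptive label does not remove a one-directional bias.
- **Table 2 already has an ad-hoc undetermined class** for invalid or missing RT-qPCR. SAP 5.2.2 does not commit to reporting it, and it is itself under-recorded.
- **The illustrative values of E and s have no anchor in the documents.** That is correct; they show direction and scale only.
- **The OR/AND point is a clarity edit.** Conventional precedence gives the intended-looking reading, but explicit brackets remove the risk in programming.

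**Conclusion.** The point holds as one about incomplete ascertainment. The ad-hoc LCD rate is a lower bound on incidence under the wider definition, and the share of the extra yield that it shows equals an unknown sampled fraction. With 40 primary cases, an assumed 10 to 20 true extra cases and a sampled fraction of 0 to 0.5, the reported rate falls short by 1.5 to 6.1 per 1000 person-years (5/3300 to 20/3300).

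This rests on three assumptions: the definition is bracketed so that protocol LCD cases are retained, the 40 primary cases are taken as complete, and E and s are illustrative. The stronger conclusion, that the analysis can show nothing about a broader definition, goes too far: added cases that are observed do establish a minimum. What cannot be concluded is that a small increment means low yield. The primary analysis is unaffected.

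**What to change.** In SAP 5.2.2 and Table 2:

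1. Report protocol LCD cases and added ad-hoc-only PCR-positive cases separately, as counts and a listing by fever arm.
2. Label any ad-hoc rate *minimum, sampled episodes only*. Beside it, show the number of recorded ad-hoc-only episodes with and without a valid RT-qPCR. Note that this count is itself incomplete, because diary data outside AFI are not routinely entered.
3. Write the definition as [(two-day arm) OR (one-day arm AND clinical suspicion)] AND RT-qPCR result.
4. Apply the same label to the ad-hoc non-LCD and undetermined classes.

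The wording on who is bled in Protocol sections 3, 6.4 (Table 3 footnote), 6.5.3.2, 6.5.5.1 and 6.7 and in SAP section 2 must be reconciled, so that the report can state which rule the available samples reflect.

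The cost is SAP wording plus one listing and one count table. The downside is that the ad-hoc rate loses its reading as a full incidence.
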